9.2.4 Relationship to study medication

Relationship to study medication will be assessed for the three treatments (GAD-Alum, etanercept and Vitamin D) separately.

Unrelated:

This category is applicable to those Adverse Events which, after careful medical consideration at the time they are evaluated, are judged to be clearly and incontrovertibly due to extraneous causes (disease, environment, etc.) and do not meet the criteria for study medication relationship listed under remote, plausible or probable.

Remote:

In general, this category is applicable to those Adverse Events which, after careful medical consideration at the time they are evaluated, are judged to be remotely related to the test study medication. An Adverse Event may be considered remote if, or when, for example: (i) it does not follow a reasonable temporal sequence from administration; (ii) it could readily have been produced by the patient's clinical state, environmental or toxic factors, or other modes of therapy administered to the patient; (iii) it does not follow a known response pattern to the suspected study medication; (iv) it does not reappear or worsen when the study medication is re-administered.

Plausible:

This category is applicable to those Adverse Events which, after careful medical consideration at the time they are evaluated, the connection with the test study medication administration appears unlikely but cannot be ruled out with certainty. An Adverse Event may be considered plausible if, or when: (i) it follows a reasonable temporal sequence from administration; (ii) it could not readily have been produced by the patient's clinical state, environmental or toxic factors, or other modes of therapy administered to the patient; (iii) it follows a known response pattern to the suspected study medication; (iv) it does not reappear or worsen when the study medication is readministered.

Probable:

This category is applicable to those Adverse Events, which, after careful medical consideration at the time they are evaluated, the connection with the test study medication administration appears to, with a high degree of certainty, be related to the test study medication. An Adverse Event may be considered probable if: (i) it follows a reasonable temporal sequence from administration; (ii) it could not be reasonably explained by the known characteristics of the patient's clinical state, environmental or toxic factors, or other modes of therapy administered to the patient; (iii) it disappears or decreases on cessation or reduction in dose. There are important exceptions when an Adverse Event does not disappear upon discontinuation of the study medication, yet study medication-relatedness exists; e.g. bone marrow depression, fixed study medication eruptions, and tardive dyskinesias; (iv) it follows a known response pattern to the suspected study medication; (v) it reappears upon re-challenge.

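### In 9.2.4 the lead sentence of the Plausible category contradicts its own criteria, and one criterion is shared with Remote, so the 10.3 summary by causality is less reliable

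*Combined protocol and SAP*

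**What the plan says.** Section 9.2.4 defines four levels: Unrelated, Remote, Plausible and Probable. Each has a lead sentence, and the last three also have numbered criteria.

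- **Plausible.** The lead sentence says that "the connection with the test study medication administration appears unlikely but cannot be ruled out with certainty". Criteria (i)-(iii) are reasonable timing, no ready alternative cause and a known response pattern. Criterion (iv) is no recurrence or worsening on re-administration.
- **Remote.** Criteria (i)-(iii) are the negatives of those three, and (iv) reads "it does not reappear or worsen when the study medication is re-administered". The list is offered as examples.
- **Probable.** The lead requires a high degree of certainty. The criteria include (ii) "it could not be reasonably explained by the known characteristics" of the patient's state and similar factors, and (iv) "it follows a known response pattern to the suspected study medication". Dechallenge (iii) and rechallenge (v) are added.
- **Unrelated.** The cause must be incontrovertibly extraneous, and such events must also be ones that "do not meet the criteria for study medication relationship listed under remote, plausible or probable".

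The alternative causes in criterion (ii) of each list include "environmental or toxic factors, or other modes of therapy administered to the patient". The section opens with: "Relationship to study medication will be assessed for the three treatments (GAD-Alum, etanercept and Vitamin D) separately".

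Section 9.2.5 requires a relationship rating for every AE. Section 10.3 summarises AEs by causality. It does not say how the three ratings enter that summary or which levels count as related.

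**The concern.** A causality scale works only if its levels are ordered and a rater can tell them apart. Here the middle level tells the rater two opposite things: the lead places the event on the unlikely side, while the criteria describe features that favour the drug. Careful medical judgement does not settle this, because the text gives that judgement two anchors.

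At stake is the breakdown of AEs by causality in 10.3, together with other relatedness judgements that use the same scale, such as the preliminary causality assessment in an initial SAE report (9.2.6). With approximately 20 patients at approximately 10 sites (6.1), each site rates about 20/10 = 2 patients, so different readings between sites have little chance to average out.

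Two secondary points concern the same section. Remote (ii) can also describe an event with an extraneous cause, which blurs its border with Unrelated. And in a trial whose first objective is tolerability of the combination (4.1), the section does not say whether one study drug may serve as the alternative explanation for another.

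**Working it through.** The plan gives no figure to reproduce here. The check is on the wording.

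**Step 1. Criteria side by side (9.2.4).**

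| Feature | Remote | Plausible | Probable |
|---|---|---|---|
| Timing | (i) not reasonable | (i) reasonable | (i) reasonable, same words as Plausible |
| Other ready cause | (ii) yes | (ii) no | (ii) no, nearly the same words |
| Known response pattern | (iii) no | (iii) yes | (iv) yes, same words as Plausible |
| Recurs on re-administration | (iv) no | (iv) no | (v) yes |
| Resolves or lessens on stopping | not listed | not listed | (iii) yes |

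Of the 4 Plausible criteria, 3 have a counterpart in Probable (2 word for word, 1 nearly so), and the same 3 are the reverse of Remote (i)-(iii). The remaining 1, criterion (iv), is Remote (iv) apart from a hyphen.

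**Step 2. What two compliant raters would do.**

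- Event A has reasonable timing, no other ready cause, a known pattern, and no recurrence at the next dose. By the criteria it is Plausible. By the lead it is not, because nothing about it makes the link look unlikely; such a rater may move it up to Probable, or down to Remote through the shared (iv).
- Event B has poor timing and another ready cause, but the rater cannot exclude the drug. By the lead it is Plausible. By the criteria it is Remote.

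The two events can move in opposite directions, so no net direction follows from the text. Read by lead sentences alone, the scale runs from remotely related, to unlikely, to highly certain, with no level for a reasonable possibility.

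**Step 3. Does the answer depend on how many criteria are needed?** Four yes/no features (timing, other cause, pattern, recurrence) give 2^4 = 16 patterns. Dechallenge is left out. The patterns were sorted on three readings:

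- Any one criterion suffices: 13 patterns meet all three of Remote, Plausible and Probable, and 3 meet two of them. None falls in a single category.
- All criteria required: 13 patterns fit none of the three, and 1 fits each (13 + 3 = 16).
- Any one for Remote (its list is given as examples), all for the other two: 14 are Remote only, 1 is Probable only, and the 1 pattern that fits Plausible also fits Remote through criterion (iv) (14 + 1 + 1 = 16).

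Only the all-criteria reading separates the levels, and it leaves most patterns unclassified. The patterns are not equally likely in patients; the count tests the wording and does not predict event numbers.

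**Step 4. Unrelated against Remote.** Eight of the 16 patterns have a ready alternative cause. If any one Remote criterion suffices, 0 of 8 avoid Remote; if all are required, 7 of 8 do. How well the boundary holds therefore depends on a rule that the text does not state.

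**Step 5. Co-administration (6.1, 8.1, 8.3).** Etanercept runs from Day 1 to 90, vitamin D from Day 1 to 450, and GAD-Alum is given on Days 30 and 60. Both GAD-Alum injections (2 of 2) and the whole etanercept period lie within vitamin D dosing. Injection-site reactions are listed as a risk of GAD-Alum (2.2) and of etanercept (2.3). If each counts as other therapy for the other, such a reaction can be discounted for both. The schedule shows where the question arises, not how often it would change a rating.

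**Step 6. Sensitivity of a percentage.** If 20 patients are enrolled, one patient who changes category moves a per-patient percentage by 1/20 = 5 points.

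**The case against.** The strongest reply is that the section is guidance, not an algorithm. Remote is worded permissively, its list is illustrative, and every level rests on medical consideration. An incontrovertible cause is a stricter standard than one that could readily have produced the event, so Unrelated and Remote can be separated by degree, and the exclusion clause formally prevents double membership. This stands. A reader might infer that Unrelated is an empty category; that follows only if a single Remote criterion is treated as sufficient, which the text does not say. Loose drafting is the most that can be claimed.

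On co-administration, the reply is that other modes of therapy is undefined and may mean non-study therapy only, and that the risk profiles are partly distinct: hypercalcaemia for vitamin D (2.4), infections and blood dyscrasias for etanercept (2.3). This also stands. A reader might infer that events will be systematically attributed away from the combination; the documents show only that they may be, with injection-site reactions as the clearest shared case.

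On consequence, none of the tolerability variables in 4.2.1 is defined by causality, 10.3 tabulates all observed AEs and SAEs, 9.2.6 requires every SAE to be reported regardless of attribution and has the CRO query inconsistencies, and no stated decision rule uses the causality split. Section 10.3 also describes itself as brief, so the absence of a per-drug table there does not prove that none is planned. All of this limits the damage.

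None of it answers the main point. Permissive wording cannot reconcile a lead sentence with criteria that say the opposite, and a criterion shared by two levels cannot tell them apart.

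**Conclusion.** The contradiction within Plausible, and the criterion it shares with Remote, are errors in an operative rating rule that feeds the 10.3 summary by causality. The Unrelated boundary and the status of the other study drugs are secondary matters of clarification.

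The error is minor. It is confined to the causality breakdown and to relatedness judgements drawn from the same scale. How many ratings would change, and in which direction, cannot be derived from the documents. The only figure available is the 5 points per reclassified patient, which assumes 20 enrolled. A reader might conclude that the primary tolerability assessment is compromised; the documents do not support that, because the all-cause counts of AEs, SAEs, infections and injection-site reactions do not use the scale.

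The conclusion assumes that sites rate from 9.2.4 as written. CRF instructions or training could remove some of the ambiguity, but they are not among the documents.

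**What to change.** In 9.2.4:

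1. Reconcile the Plausible lead with its criteria. The documents do not show which of the two is the drafting error. If the criteria are what was meant, the lead could read: *a reasonable possibility, but not established with a high degree of certainty*.
2. Remove or replace Plausible (iv), and state for each level whether any or all criteria are needed. Without (iv), the Plausible list is essentially a subset of the Probable list, so the two then differ by the certainty in the lead and by the dechallenge and rechallenge criteria. The any-or-all rule should also cover an event with reasonable timing but a possible other cause.
3. Delete Remote from the exclusion clause of Unrelated, so that these two levels differ by degree of certainty.
4. State that an event attributed to another study drug must not end up as not related to the combination. Raters should remain free to weigh the other study drugs in each per-drug rating, since that is the purpose of rating separately.

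In 10.3, tabulate causality per drug plus one rating for the combination, and define which levels count as related. Taking the highest of the three per-drug ratings is not enough: if all three have been discounted to Remote, the highest is still Remote.

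The cost is protocol wording, one extra table and possibly one rating field for the combination. Whether a new field is needed cannot be settled without the CRF. No dose, visit or procedure changes.

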9.2.5 Reporting of Adverse Events

All Adverse Events must be recorded in the CRF, defining relationship to study medication, severity and seriousness. Adverse Events should also be recorded by the investigator in the patient file/notes.

9.2.6 Timelines and Reporting of SAE

All SAEs must be reported, whether or not considered attributable to the study drug on a separate SAE Report Form.

An assigned CRO, contracted by Diamyd Medical AB, will be responsible for reporting all Serious Adverse Events (SAEs) in accordance with ICH Good Clinical Practice and local regulations. The sponsor, Diamyd Medical AB and the assigned CRO will complete and sign a "Pharmacovigilance Working Instructions" agreement covering the safety reporting responsibilities in the study. This agreement will also ensure the sponsor and Diamyd Medical AB is directly informed of each SAE reported by the Investigators.

In order to meet the specified reporting requirements investigators should adhere to the following process for recording and reporting SAEs.

It is the investigator's responsibility to, as soon as he/she is aware of a potential Serious Adverse Event (SAE), he/she should contact the assigned CRO by fax or e-mail, and in any case no later than 24 hours after the knowledge of such a case.

At the time of initial reporting, the investigator must provide as a minimum requirement, the patient number, birth date, nature of the SAE, and a preliminary assessment of causality. The investigator should follow-up the initial notification of the potential SAE by faxing or e-mailing a copy of the SAE reporting form to the assigned CRO at the numbers/e-mail address provided in the investigator Site File and on the SAE Report Form. The faxed/e-mailed SAE Reporting Form should be received by the assigned CRO within 24 hours of the initial notification of the event.

It is the investigator's responsibility to report to the CRO follow-up information on an existing SAE that is fatal or life-threatening within 5 days after the initial report. Where appropriate, hospitalisation or autopsy reports should be made available. All Serious Adverse Events will be followed up until resolution (i.e., asymptomatic, stabilisation or death).

It is the CRO's responsibility to receive e-mail or fax copies of the SAE report form and other relevant CRF pages from the Investigators. The Drug Safety unit at the CRO will review the information provided on the form and enter it into the safety data base. The SAE report will be assigned a unique number that will be entered on the SAE Report Form, and will be used to identify the report in all future communication. A notification of receipt of the report will be sent to the reporter, either by fax or e-mail within 48 hours. The CRO will contact the Investigator directly if there is any inconsistencies and missing information.

The CRO is responsible for the timely submission of Suspected Unexpected Serious Adverse Reactions (SUSARs) to the Competent Authority and Ethics Committee according to appropriate Competent Authority and Ethical Committee requirements. It is the CRO's responsibility to report SUSARs to investigators according to ICH Good Clinical Practice and to local regulations and to notify the Competent Authorities will be notified of all SUSARs through the Eudravigilance database.

Fatal and life-threatening SUSARs should be reported by the assigned CRO as soon as possible to the Competent Authorities and Ethical Committees, and in any case no later than seven (7) calendar days, after knowledge by the Sponsor/assigned CRO of such a case. Relevant follow-up information on the case will be subsequently communicated within an additional eight (8) days. All other SUSARs shall be reported to the Competent Authorities concerned and to the Ethics

Committee concerned as soon as possible but within a maximum of fifteen (15) days of first knowledge by the assigned CRO/Sponsor.

9.2.7 Unresolved Events

If an AE/SAE is present when the patient has completed the study the course of the event must be followed until final outcome is known or the condition is stable.

9.2.8 Pregnancy Report Form

Pregnant and lactating women will not be included in the study. Menarchal females must have a negative urine pregnancy test prior to randomization and a negative urine pregnancy test at each study visit with study drug administration, prior to injection of study drug. Patients will be required to use an adequate form of birth control during the study. At Visit 2 the need for birth control will be re-assessed. Patients and their partners will be strongly advised to avoid pregnancy for 1 year following the last dose and instructed to use adequate birth control.

A pregnancy occurring during the trial must be recorded on the Pregnancy Report Form and no further drug doses will be given. If the pregnancy is verified prior to any of the injections, no further injection shall be given.

The Pregnancy Report Form should be faxed or e-mailed within 24 hours of awareness to the assigned CRO. A copy of the report should be filed at the study site for follow-up until delivery. Any pregnancy must be followed until delivery or to the end of pregnancy.

10 Statistical Methodology and Data Management

10.1 Study Design

The EDCR IIa study is an open controlled pilot intervention trial of the safety, and evaluation of the immune system response and residual insulin secretion, by a combined treatment with etanercept, Vitamin D and GAD-Alum (Diamyd).

Study Participants:

Newly diagnosed classic type 1 diabetes patients: N=20. Age 8.00-17.99 years. Recruited from approximately 10 pediatric clinics in Sweden

10.2 Estimation of Sample Size

Power analysis:

No formal power analyses is done for this pilot study

10.3 Statistical Analysis Plan

In brief the following analysis is planned:

All continuous variables will have the following descriptive statistics displayed: number of observations (n), mean value, standard deviation, minimum, median, and maximum. All variables Confidential

of a categorical nature will be displayed with frequencies and percentages. The tabulation of the descriptive statistics will be split by treatment group and visit. Where appropriate, baseline (screening) descriptive statistics will also be included.

Demographic and other baseline characteristics

Demographics such as age and gender will be described for Intention-to-treat and the Total population. Measures for other baseline characteristics are medical history, current medical conditions (at baseline), and current diabetes medication (at baseline). The baseline characteristics will be presented for the safety population. Demographics and baseline characteristics will be presented using descriptive statistics (summary tables).

Variables:

The AE/SAE data will be presented using a standardized tabulation of the frequency and incidence rate of all observed AEs/SAEs. The frequencies and incidence rates are calculated on a per patient basis. Adverse events will be summarized by body system, causality, and severity. Other safety data will be presented by descriptive statistics. Data regarding C-peptide and immune system as well as Adverse events and other safety data will be summarized descriptively.

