4.2 Endpoints

4.2.1 Primary endpoints

Primary endpoints:

To Evaluate the tolerability of a combination therapy with Diamyd, Vitamin D and etanercept at Month 6 (main study Period), 9, 15 and 30 (extension study period)

Variables to evaluate tolerability:

- Reactions of the injection site
- Infections
- Occurrence of Adverse Events (AEs)
- Occurrence of Serious Adverse Events
- Physiological and Neurology assessments
- Laboratory measurments (biochemistry and haematology), including Calcium and Vitamin D in serum
- GAD65AB titer (GADA)

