8.1 Study Medications

The following medication supplies will be used in the study:

A. Study medication:	GAD-Alum (Diamyd) subcutaneous injection Dosage and interval: 20 µg will be given subcutaneously at two occasions with one month interval (at Days 30 and 60).
IMP supplier:	Diamyd Medical AB, Stockholm, Sweden.
B. Study Medication	Etanercept (Enbrel) Dosage and interval: 0.8 mg/kg body weight, max 50 mg, given subcutaneously once per week from Day 1-90
IMP supplier	Commercially available
C Study Medication	Vitamin D (Calciferol) in oral solution Dosage and interval: 2 000 IU daily for 450 days
IMP supplier	Commercially available

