10.4 Study Populations

Intention-to-treat population

Patients will be included in the primary intention-to-treat population for analysis of efficacy if they receive at least 1 dose of all study drugs, and are assessed at a later visit.

Per protocol population

In order to qualify for the stringent per protocol population, the subjects must have followed the study protocol without any major violations. Any examinations missed will be substituted with the last observation carried forward, but examinations from not more than 1 visit may be lost.

Total population

Any patient who withdraws from the study will be included in the safety analysis (adverse events and safety parameters). Data for all patients will be listed, and a list of withdrawn patients, with all reasons for withdrawal, will be given.

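### Section 10.3 puts adverse events on a per-patient basis, leaves the incidence-rate denominator undefined and plans no event counts, so the summary may not show recurrence of injection-site reactions and infections

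*Combined protocol and SAP*

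**What the plan says.** Section 10.3 plans a "standardized tabulation of the frequency and incidence rate of all observed AEs/SAEs" and then sets the unit: "The frequencies and incidence rates are calculated on a per patient basis". It adds: "Adverse events will be summarized by body system, causality, and severity". It states no number of events, events per child, reactions per injection or patient-time, and it does not define incidence rate.

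Three other statements bear on the point.
- Section 10.3, on descriptive tables generally: "The tabulation of the descriptive statistics will be split by treatment group and visit".
- Section 10.3, on safety data other than adverse events: "Other safety data will be presented by descriptive statistics".
- Section 10.4, on listings: "Data for all patients will be listed".

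Section 4.2.1 opens its list of primary tolerability variables with "Reactions of the injection site", followed by infections. Occurrence of adverse events is a separate item in the same list. Etanercept is "given subcutaneously once per week from Day 1-90" (section 8.1), and GAD-Alum is injected at Visits 3 and 4 (section 6.2.2). Section 9.2.5 requires every adverse event to be entered in the CRF.

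**The concern.** Tolerability is the primary objective. For a weekly injection it depends on how often a reaction occurs as well as on whether one ever occurred. For infections, repeated episodes in one child mean something different from single episodes in several children. A count of children with at least one event cannot show either. If most children have an event, the percentage also approaches 100% and stops responding to the burden.

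The protocol expects these events. Section 2.3 lists injection-site reactions and infections among the most commonly reported side effects of etanercept, and section 2.2 reports site reactions with Diamyd. Section 3 says the results will inform the design of a larger Phase II trial, which would need event burden as well as the share of children ever affected.

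**Working it through.** The plan gives no event rate, power or sample-size calculation (section 10.2), so there is no figure of its own to reproduce.

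**Inputs from the documents.** 20 children (section 10.1). Weekly etanercept on Days 1 to 90 (section 8.1) means Days 1, 8, ..., 85, which is 13 injections per child and up to 20 × 13 = 260 in all. GAD-Alum: 2 injections per child.

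**Assumption.** The reaction probability per injection, p, is not in the documents. A range is shown.

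**Step 1: an example that needs no rate model.**
- Six children react once each: 6/20 = 30% of children, 6/260 = 2.3% of injections.
- Six children react to all 13: 6/20 = 30% of children, 78/260 = 30% of injections.

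The per-patient figure is the same in both cases.

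**Step 2: how much a yes/no per child keeps.** Assume independent reactions with the same p at each injection. The chance of at least one is q = 1 − (1 − p)^13. The Fisher information on p is [13(1 − p)^12]² / [q(1 − q)] from the yes/no value and 13 / [p(1 − p)] from the count. Their ratio simplifies to 13p(1 − p)^12 / q.

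| p per injection | reactions per child (13p) | children with ≥1, of 20 (20q) | information kept |
|---|---|---|---|
| 0.01 | 0.13 | 2.4 | 94% |
| 0.02 | 0.26 | 4.6 | 88% |
| 0.05 | 0.65 | 9.7 | 72% |
| 0.10 | 1.3 | 14.9 | 49% |
| 0.20 | 2.6 | 18.9 | 19% |
| 0.30 | 3.9 | 19.8 | 5.5% |

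The ratio equals 50% at p ≈ 0.098, which is about 1.28 reactions per child, with about 74% of children reacting at least once.

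**Step 3: saturation at high rates.** From p = 0.30 to 0.50, expected reactions rise from 260 × 0.30 = 78 to 260 × 0.50 = 130. Children affected move only from 19.8 to 20.0 of 20. With strong clustering within children (beta-binomial, correlation 0.2) they move from 17.4 to 19.5.

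**Step 4: infections.** These have no per-injection denominator, so the 13-injection model does not apply. For a Poisson count with mean μ per child, the share kept is μ/(e^μ − 1), which equals 50% at μ ≈ 1.26. If children differ strongly in their rates (negative binomial, known shape k), the share is [μk/(k + μ)] × P0/(1 − P0), with P0 = [k/(k + μ)]^k. For k = 1 it is 50% at μ = 1. For k = 0.5 it is 60% at μ = 0.5 and 46% at μ = 1.

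**Step 5: what the visit split would recover.** If it covers the adverse event tables, the 13 injections fall into three intervals: 5 before Visit 3, 4 before Visit 4 and 4 before Visit 5. A child reacting to all 13 would appear at three visits, and a child reacting once would appear at one.

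**The case against.** The case against has several parts, and some of it stands.

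- **The plan does not say that repeated events are collapsed.** A reader might infer a stated rule of counting each child once. The text refers to all observed events and leaves incidence rate undefined, so events per patient is a possible reading. Patients with an event is the more natural one, but it remains an interpretation.
- **The two variables are listed apart from adverse events.** The per-patient sentence may not govern them. If it does not, what remains is a general promise of descriptive statistics, and event counts are still unplanned.
- **The visit split and listings keep some recurrence.** This is true in part. The split reduces 13 possible reactions to at most three, and section 10.3 does not clearly apply it to adverse event tables. For the two GAD-Alum injections, given at separate visits, a by-visit table would come close to a per-injection figure. With 20 children the listings can be read by eye, but they are not a summary.
- **Per-patient counting is conventional, and section 10.3 is only a brief outline.** Both are true. No decision rule depends on this table. The proposal keeps the patient count and adds to it.
- **Per-injection data on etanercept may not exist.** The diary instruction on site reactions (section 6.6) names only the Diamyd injections, and scheduled site inspection (Table 2, section 7) is tied to GAD-Alum. This stands and limits the fix.

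**Conclusion.** The point holds as a gap in specification. Section 10.3 sets a per-patient unit, does not define the incidence-rate denominator and plans no event counts. On the natural reading, the summary of the recurrent primary tolerability variables cannot distinguish one event from many in the same child.

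The size of the loss is not known. A reader might infer that these variables lose most of their information, but the documents give no reaction or infection rate to support that. More than half is lost only above about 1.3 events per child under independence, or at about 1 or somewhat fewer if children differ strongly in their rates. At 2% or 5% per injection the yes/no figure keeps 88% or 72%. The 13-injection arithmetic concerns etanercept site reactions and says nothing about infections.

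No sample size or power figure changes. This is a low-cost improvement to the primary safety summary.

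**What to change.** In section 10.3:

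1. Keep the number and percentage of children with at least one event. Beside it, add the number of events and the events per child (median, range) for all adverse events, infections and injection-site reactions.
2. Define the incidence-rate denominator, using patient-time for infections.
3. Report site reactions per injection given for GAD-Alum. Do the same for etanercept only if the CRF records reactions so that they can be linked to injections. Check this before committing to it.

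The event counts use adverse events that section 9.2.5 already requires in the CRF. It should not be assumed that the etanercept per-injection figure needs no new data. Otherwise the cost is slightly longer tables.
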